1.3 Secondary Objectives

- Determine progression-free survival (PFS) and duration of response. Evaluate safety of this combination in relapsed/refractory indolent NHL patients
- To perform correlative laboratory studies using on-treatment peripheral blood samples and post-treatment tumor samples to quantify the binding of Imprime PGG to neutrophils and correlate with treatment response.

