8. CORRELATIVE/SPECIAL STUDIES

Participants will have one pretreatment peripheral blood sample collected within one week of starting treatment, 4 post-treatment peripheral blood samples collected approximately one hour following the completion of both infusions (one on each infusion day), and 3 pre-treatment blood samples collected at the time of routine lab collection on days 8, 15, and 22. Fresh whole blood samples will be processed in the laboratory of [name] and Biothera will provide the funding necessary to complete this work. Using reagents and a flow cytometric protocol provided by Biothera, we will quantify the percentage of Imprime PGG-bound and unbound neutrophils following each weekly treatment. Preclinical evaluation of healthy subjects, and cancer patients participating in Imprime PGG studies, demonstrate that based on the ability of Imprime PGG to bind to neutrophils and monocytes, subjects can be categorized into (i) binders- in which Imprime PGG bound to 5% or more of the total neutrophil population and (ii) low or non-binders- in which Imprime PGG bound to less than 5% of total neutrophils. We will correlate the percentage of Imprime PGG bound neutrophils with treatment response. Flow cytometric analysis of pre- and post-treatment changes in neutrophil activation marker expression using antibodies against CD11a, CD11b, CD63, CD87 and CBRM1/5 will also be performed.²⁵ This flow cytometric profile was used to quantify the proportion of activated neutrophils in whole blood before and after immunotherapy with an anti-tumor monoclonal antibody and GM-CSF in patients with neuroblastoma. All five markers of neutrophil activation were upregulated following treatment, and the degree to which they were upregulated correlated with outcome as reflected by progression-free survival. We will use this profile to quantify the proportion of activated neutrophils pre- and post-therapy on our study and correlate this with treatment response.

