14. STATISTICAL CONSIDERATIONS

14.1 Study Design/Endpoints

This is an open-label, single-arm, phase II clinical trial of Imprime PGG in combination with rituximab in patients with relapsed/refractory indolent B cell non-Hodgkin lymphomas. The primary endpoint is efficacy as measured by overall response rate. Secondary endpoints will include response duration, progression free survival at 1 year, , and rate of grade III and IV adverse events or discontinuation due to toxicity. We will estimate the proportion of patients alive without progression at 12 months after study entry. All patients must be followed for a minimum 12 months and must have scans at 6 and 12 months. No patients will be censored for this assessment. The one-year rate of being alive without progression will be estimated as a binomial proportion, and an exact binomial 90% confidence interval will be provided.

Patients will be accrued in a single stage design, with a goal accrual of 25 patients. Assuming a 30% response rate with rituximab alone, if the true but unknown rate of CR or PR is 50% with the addition of Imprime PGG, the probability of observing 11 or more patients with a response is 0.79. Therefore a study with 25 patients, in which an observed response rate of 11/25 (44%) would be considered worthy of further consideration.

We propose correlative studies quantifying Imprime PGG-bound and activated neutrophils, comparing both to the number and activation of unbound neutrophils from the same patient. We can examine the association between response to therapy (CR/PR vs. SD/Progression as best response).

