14.3 Sample Size/Accrual Rate

The planned sample size is 25 patients. Based on historical rates, accrual will be complete in 24 months. The total anticipated duration of the study, after the first patient is enrolled, will be approximately 36 months.

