17.3 APPENDIX C: RESPONSE CRITERIA FOR LYMPHOMA

(adapted from the International Harmonization Project for Lymphoma Criteria²⁶)

Response	Definition	Nodal masses	Spleen/liver	Bone Marrow
Complete Response (CR)	Disappearance of all evidence of disease	(a) For FDG-avid or PET positive prior to therapy; mass of any size permitted if PET negative (b) For variably FDG-avid or PET negative; regression to normal size on CT	Not palpable, nodules disappeared	Infiltrate cleared on repeat biopsy; if indeterminate by morphology, immunohistochemistry should be negative
Partial Response (PR)	Regression of measurable disease and no new sites	≥50% decrease in SPD of up to 6 largest dominant masses; no increase in size of other nodes (a) FDG-avid or PET positive prior to therapy; one or more PET positive at previously involved site (b) Variably FDG-avid or PET negative; regression on CT	≥50% decrease in SPD of nodules (for single nodule in greatest transverse diameter); no increase in size of liver or spleen	Irrelevant if positive prior to therapy; cell type should be specified
Stable Disease (SD)	Failure to attain CR/PR or PD	(a) FDG-avid or PET positive prior to therapy; PET positive at prior sites of disease and no new sites on CT or PET (b) Variably FDG-avid or PET negative; no change in size of previous lesions on CT		
Relapsed or Progressive Disease (PD)	Any new lesion or increase by ≥50% of previously involved sites from nadir	Appearance of a new lesion(s) >1.5cm in any axis, ≥50% increase in SPD of more than one node, or ≥50% increase in longest diameter of a previously identified node >1cm in short axis Lesions PET positive if FDG-avid lymphoma or PET positive prior to therapy	>50% increase from nadir in the SPD of any previous lesions	New or recurrent involvement

CONFIDENTIAL

This document is confidential. Do not disclose or use except as authorized.

Imprime PGG and rituximab for relapsed indolent NHL

November 13, 2018

Abbreviations: PET, positron emission tomography; CT, computed tomography; SPD, sum of the product of the diameters.

CONFIDENTIAL

This document is confidential. Do not disclose or use except as authorized.

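### Section 14.1 codes response for the neutrophil correlations in two classes only, although Appendix C and the planned CTs already supply four ordered grades and measured tumour change

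*Combined protocol and SAP*

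**What the plan says.** Section 1.3 makes it a secondary objective to "quantify the binding of Imprime PGG to neutrophils and correlate with treatment response". Section 8 keeps binding as a percentage: "We will correlate the percentage of Imprime PGG bound neutrophils with treatment response". Section 8 also plans to correlate the proportion of activated neutrophils with response. It gives no response coding for either analysis.

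The coding appears only in Section 14.1: "We can examine the association between response to therapy (CR/PR vs. SD/Progression as best response"). That sentence does not name the second variable. No test, significance level, effect size or power is given for the correlative work, and no ordered or continuous response analysis is planned.

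Appendix C defines complete response (CR), partial response (PR), stable disease (SD) and progressive disease (PD). For nodal masses, PR requires "≥50% decrease in SPD of up to 6 largest dominant masses". CTs are scheduled at baseline, 10 weeks after treatment, and at 6 and 12 months. On size, "The planned sample size is 25 patients" (Section 14.3).

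**The concern.** Cutting response in two puts a 49% shrinkage in the same class as progression and a 51% shrinkage in the same class as complete remission. The primary endpoint needs that cut, because its 30% comparator is itself a response rate. A biomarker correlation does not need it, and the response criteria do not require it for that purpose.

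In a single-arm trial the overall response rate (ORR) separates the contribution of Imprime PGG from that of rituximab only by reference to an assumed historical rate. The relation between binding and response is therefore important within-trial evidence on the proposed mechanism. With 25 patients, discarding outcome information makes a real relation easier to miss.

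**Working it through.** **Inputs from the documents.** n = 25 (Section 14.3). Response rates are 30% ("Assuming a 30% response rate with rituximab alone"), 50% ("if the true but unknown rate of CR or PR is 50% with the addition of Imprime PGG") and 11/25 = 44%, the bar for further interest (Section 14.1). The CR rate is about 7% for rituximab alone (Section 2.3).

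**Assumptions, because the documents give none.** Two-sided alpha is 0.05. Marker and tumour change are bivariate normal with correlation ρ from 0.2 to 0.7. The four grades are CR 7% or 20%, PD 15% and SD 35% at 50% ORR.

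**The plan's own figure.** Section 14.1 states that "the probability of observing 11 or more patients with a response is 0.79". Exact binomial: P(X ≥ 11 | 25, 0.50) = 0.788, which agrees. The type I error at 30% is 0.098. This is the plan's only power figure, and it concerns the primary endpoint.

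**Simulated power.** 20,000 trials per cell. Spearman correlation was used for continuous change and for grades, and a rank test of the marker for two classes. Null rejection was 0.049-0.052, so the methods are compared at equal size.

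| ρ | Continuous change | Four grades, ORR 50% | Two classes, ORR 50% | Two classes, ORR 44% | Two classes, ORR 30% |
|---|---|---|---|---|---|
| 0.2 | 0.145 | 0.137-0.142 | 0.118 | 0.114 | 0.104 |
| 0.3 | 0.275 | 0.255-0.262 | 0.208 | 0.204 | 0.181 |
| 0.4 | 0.470 | 0.426-0.435 | 0.335 | 0.333 | 0.300 |
| 0.5 | 0.690 | 0.632-0.653 | 0.517 | 0.510 | 0.456 |
| 0.6 | 0.868 | 0.821-0.838 | 0.706 | 0.699 | 0.638 |
| 0.7 | 0.966 | 0.942-0.953 | 0.868 | 0.861 | 0.809 |

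**Loss from two classes against continuous change, in points (ORR 50 / 44 / 30%).**
- ρ 0.2: 2.7 / 3.1 / 4.1
- ρ 0.3: 6.7 / 7.1 / 9.4
- ρ 0.4: 13.5 / 13.7 / 17.0
- ρ 0.5: 17.3 / 18.0 / 23.4
- ρ 0.6: 16.2 / 16.9 / 23.0
- ρ 0.7: 9.8 / 10.5 / 15.7

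Repeat runs move these by about a point, hence the rounded ranges in the conclusion.

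**Gain from four grades over two classes at ORR 50%.** 9.1-10.0 points at ρ 0.4, 11.5-13.6 at ρ 0.5 and 11.5-13.2 at ρ 0.6.

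**Analytic check at ρ = 0.5.** Cutting a normal variable so that a share p responds multiplies the correlation by φ(z)/√(p(1−p)).
- p = 0.5: 0.3989/0.5 = 0.798, so r = 0.399. With Fisher's z, 0.422 × √22 = 1.98 and power ≈ Φ(1.98 − 1.96) = 0.51.
- p = 0.3: 0.3477/√0.21 = 0.759, so r = 0.379. Then 0.399 × √22 = 1.87 and power ≈ Φ(−0.09) = 0.47.
- Uncut: Spearman's ρ is (6/π)·arcsin(0.25) = 0.483. Then 0.526 × √(22/1.06) = 2.40 and power ≈ Φ(0.44) = 0.67.

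All three are within about two points of the simulation.

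**Sensitivity, ρ 0.4-0.6.** At alpha 0.10 the loss is 12-16 points (ORR 44-50%) or 17-20 (30%). With n = 20 at alpha 0.05 it is 10-18 or 13-24. Tying the lowest 15% at a worst rank costs the continuous analysis under 1 point. If Section 8's 5% binder threshold were also applied (Fisher's exact test, ORR 50%, 30-50% binders assumed), power at ρ 0.5 would be only 0.26-0.33.

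**The case against.** The strongest reply is that Section 14.1 is permissive. It says the association can be examined and names no test, and Section 8 leaves response uncoded, so a finer analysis is not forbidden. CR/PR also matches the primary endpoint and is easy to read with 25 patients. It stands that the plan does not commit to a particular two-class test. But the sentence is the only statistical text for a secondary objective. Following it loses information, and departing from it means choosing the coding after the data are seen.

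A second reply is that the simulation treats response as an exact cut of one continuous variable. Appendix C also uses new lesions, growth of single nodes, spleen and liver findings, and marrow. This stands: the gain from SPD change is idealised, and splenic marginal zone lymphoma is eligible. It is also true that SPD change at 10 weeks is a different outcome from best response, which can draw on later scans. Both points favour ordered best response as the leading analysis.

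Four stronger readings are tempting but unsupported.
- **A loss of 15-25 points throughout.** No correlation appears in the documents. Losses above 20 points need an ORR near 30% with ρ of about 0.5-0.6, and at ρ 0.2 the loss is 3-4 points.
- **The trial's only internal test of mechanism.** Section 8 also plans anti-beta-glucan antibody analyses and pre/post activation-marker comparisons.
- **Activation as part of the secondary objective.** Section 1.3 names binding only; activation enters in Sections 8 and 14.1.
- **A finer outcome would make the analysis well powered.** It would not: power with continuous change is about 0.28 at ρ 0.3 and 0.47 at ρ 0.4.

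**Conclusion.** The point holds as a cheap improvement. The only stated response coding discards ordering and magnitude that the planned assessments already provide. With n = 25, a two-sided 5% rank test and ρ of 0.4-0.6, the cost against continuous tumour change is about 13-18 points of power at 44-50% ORR and up to about 23 at 30%. It is about 7-10 points at ρ 0.3 and 3-4 at ρ 0.2. Four ordered grades alone recover about 9-14 points at 44-50% ORR for ρ 0.4-0.6. These sizes rest on assumed correlations, alpha and grade shares, not on figures in the plan. A null result would remain hard to interpret if the true relation is weak. The primary ORR and the 11/25 rule are unaffected.

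**What to change.** Replace the last sentence of Section 14.1 with text along these lines:

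- **Leading analysis.** Relate the continuous percentage of Imprime PGG-bound neutrophils, and separately of activated neutrophils, to best response in four ordered grades (CR > PR > SD > PD) by Spearman rank correlation. Name one post-infusion sample or one summary as the predictor, since Section 8 yields up to eight samples per patient, and one summary of the five activation markers.
- **Second analysis.** Relate the same predictors by rank correlation to percent SPD change from baseline to the 10-week CT. Give the worst rank to patients with new lesions, or with progression or death before that CT. State a rule for a CT missing for any other reason.
- **Description.** Keep CR/PR versus SD/PD as a descriptive summary.
- **Limits to state.** The SPD analysis uses the 10-week CT rather than best response, and it does not capture spleen, liver or marrow criteria.

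Leave the primary ORR and the 11/25 rule as they are.

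**Cost.** A few sentences in Section 14.1. The ordered-grade analysis keeps the plan's best-response definition and needs no new data. The SPD analysis needs SPD values on the case report form; Section 12.1.2 lists a response form but not its contents. No extra scan, sample, visit or patient is required.

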14.2 Early Stopping- Toxicity

If 3 or more participants experience a grade 4 non-hematologic toxicity, the study will be suspended and the data will be reviewed by the data monitoring committee.

CONFIDENTIAL

This document is confidential. Do not disclose or use except as authorized.

Additionally, if at any point in the study any participant experiences a grade 5 toxicity, the study will be suspended and the toxicity data including attribution will be carefully reviewed. If these toxicity events are determined to be at least possibly related then the study will close.

[name] reserves the right to discontinue the study at any time.

14.3 Sample Size/Accrual Rate

The planned sample size is 25 patients. Based on historical rates, accrual will be complete in 24 months. The total anticipated duration of the study, after the first patient is enrolled, will be approximately 36 months.

14.4 Reporting and Exclusions

The primary analysis will be performed on all evaluable patients.

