1. OBJECTIVES

1.1 Study Design

This is a Phase 2 open label single arm study employing a single stage design to assess efficacy and safety of Imprime PGG in combination with rituximab in relapsed/refractory indolent B cell non-Hodgkin lymphomas (NHL). The study drug, Imprime PGG, will be administered intravenously at a dose of 4mg/kg weekly for 4 weeks. Rituximab will be administered intravenously by institutional standards concurrently at a dose of 375mg/m² weekly for 4 weeks. Response will be assessed with CT scans 10 weeks +/- 3 days following the completion of treatment.

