The overall response rate for rituximab monotherapy in relapsed low-grade B-cell lymphoma is approximately 24-36% with complete response rates of approximately 7%.¹⁵ Several mechanisms for rituximab resistance have been proposed including variable CD20 expression by lymphoma subtype, variability in complement activation, and polymorphisms in Fc receptors.¹⁶⁻¹⁸ Novel agents that overcome these resistance mechanisms might offer similar complete response rates to combined chemotherapy and immunotherapy with improved tolerability.

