5.6 Criteria for Removal from Study Treatment

Participants will be removed from study when any of the criteria listed in Section 5.4 applies. The reason for study removal and the date the participant was removed must be documented in the study-specific case report form (CRF). Alternative care options will be discussed with the participant.

In the event of unusual or life-threatening complications, participating investigators must immediately notify the Principal Investigator, [name]. at [contact].

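### The primary response rate is analysed on evaluable patients, a term left undefined, while the only go rule is 11 of 25, so treated patients without a response CT could leave the denominator

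*Combined protocol and SAP*

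**What the plan says.** Section 14.4, headed as covering exclusions, consists of one sentence: "The primary analysis will be performed on all evaluable patients". The available text does not define evaluable. A short part between sections 14.4 and 15 was not available, but the table of contents lists only section 14.5, on disclosures and confidentiality, at that place.

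Section 14.1 gives the only decision rule, in two forms. One is a count: at a true response rate of 50%, "the probability of observing 11 or more patients with a response is 0.79". The other adds a rate: "Therefore a study with 25 patients, in which an observed response rate of 11/25 (44%) would be considered worthy of further consideration". The reference value is set by "Assuming a 30% response rate with rituximab alone". No type I error rate is stated. Section 14.3 repeats the sample size of 25, with no allowance for drop-out and no replacement rule.

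On timing, section 1.1 says "Response will be assessed with CT scans 10 weeks +/- 3 days following the completion of treatment". Several sections let patients leave before then:

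- Section 5.6: "Participants will be removed from study when any of the criteria listed in Section 5.4 applies".
- Section 6.3.1 removes patients with life-threatening infusion reactions from study, and section 6.4 does the same for patients who cannot tolerate either drug.
- Section 15 times the first analysis to when every patient has either reached the End of Study visit or come off study.

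Appendix C defines complete response, partial response, stable disease and progression. It has no category for a patient without a scan. The no-censoring statement in section 14.1 covers only the 12-month progression-free proportion.

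**The concern.** The plan does not settle how a treated patient with no response CT enters the primary endpoint. That patient may be a non-responder or may be left out altogether. Evaluable can reasonably mean any dose received, full treatment received, or a post-baseline scan obtained, and each meaning gives a different denominator.

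The rule was worked out for a denominator of 25. If fewer patients are analysed, the count of 11 and the rate of 44% are no longer the same rule. With no control arm, the go decision rests on this one proportion. An open-label trial that leaves the denominator open allows it to be settled after the responses are known. If the patients left out are mainly non-responders, the reported rate goes up without any more responses having occurred.

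**Working it through.** **Inputs.** From section 14.1: n = 25, go if there are 11 or more responders (44%), reference rate 0.30, target rate 0.50. The number m of treated patients left out of the denominator is an assumption, taken from 1 to 5, because the documents give no figure for it.

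**Step 1: reproduce the plan's figure.** With X ~ Bin(25, p), the probability of a go is P(X ≥ 11) = Σ C(25, x) p^x (1 − p)^(25 − x) for x = 11 to 25.

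- At p = 0.50: 0.788. The plan's 0.79 reproduces.
- At p = 0.30: 0.098. This is the false-go probability implied by the rule; the plan does not state it.

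**Step 2: count against rate.** With 22 patients analysed, 10 responders give 10/22 = 45.5%. That is above 44% but below 11 responders. The same 10 responders over all 25 patients are 10/25 = 40%, which fails both forms.

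**Step 3: leave out m non-responders, with no replacement.** Take 0.30 as the response rate among all 25 treated patients. Removing non-responders changes the denominator but not the number of responders, so X is still Bin(25, 0.30). Under the 44% cut the number needed is r = the smallest integer at or above 0.44 × (25 − m).

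| m | Analysed | 0.44 × analysed | r | P(X ≥ r), p = 0.30 |
|---|---|---|---|---|
| 0 | 25 | 11.00 | 11 | 0.098 |
| 1 | 24 | 10.56 | 11 | 0.098 |
| 2 | 23 | 10.12 | 11 | 0.098 |
| 3 | 22 | 9.68 | 10 | 0.189 |
| 4 | 21 | 9.24 | 10 | 0.189 |
| 5 | 20 | 8.80 | 9 | 0.323 |

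**Step 4: keep the count of 11.** Then r = 11 for every m and X is unchanged, so the false-go probability is 0.098 throughout. Only the reported percentage moves.

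**Step 5: what counting the unassessed as non-responders costs.** If the m patients would not have responded anyway, the false-go probability stays at 0.098 and power at 0.788. If scans are missing for reasons unrelated to response, responders come only from the 25 − m assessed, and power is P(X ≥ 11) with X ~ Bin(25 − m, 0.50):

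- m = 1: 0.729
- m = 2: 0.661
- m = 3: 0.584

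**The case against.** The strongest reply is that few patients may be affected. Section 5.6 is headed as removal from study treatment, and removal need not mean that no CT is done. Section 5.5 follows patients who have had at least one dose of both drugs for a year and times the post-treatment visit from the last day of treatment, so early stoppers stay on the schedule. Section 14.1 adds: "All patients must be followed for a minimum 12 months and must have scans at 6 and 12 months". This stands, and it is the main reason the point is minor. It does not close the gap. The plan still has no rule for a patient without the 10-week CT, and does not say whether a later scan may take its place.

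A second reply is that section 14.1 gives the rule first as a count, and under the count nothing is inflated. That also stands (step 4). But the same section gives 44% as well, and an analysis on evaluable patients naturally reports a rate.

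Two stronger readings are tempting. A reader might infer that the trial's false-positive rate is inflated as planned. The documents do not support this: without replacement, inflation needs the 44% reading and at least three excluded non-responders, no type I error rate is claimed, and the threshold is a screen for further study. Loss unrelated to response would not bias the rate upward.

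A reader might also infer that the evaluable-only rate is necessarily biased against the 30% reference. The documents do not say whether that figure, or the range of about 24-36% in section 2.3, counts unassessed patients as failures. If it leaves them out too, the comparison is like with like. The adverse-event discontinuation range of 0% to 49% in section 2.1.3 does not settle how many scans will be missed: it comes from other regimens, and stopping treatment is not the same as missing a scan.

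**Conclusion.** The point holds as a minor one. The primary analysis population is undefined in the available text, and the only go rule is written for a fixed 25 patients in two forms that can disagree once the denominator changes. The plan's power calculation is correct.

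The false-go probability about doubles, from 0.098 to 0.189, with three or four non-responders dropped, and roughly triples, to 0.323, with five. This assumes that those dropped are non-responders, that they are not replaced, and that 44% is the operative cut. With one or two dropped, or with the count of 11, it does not move. How many patients would be dropped is unknown and may be few. What remains in every case is a denominator that could be chosen after the data are seen.

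**What to change.** In section 14.4, make the primary analysis set all patients who received any dose of study treatment. Count those without a response assessment as non-responders, saying whether a later scan qualifies as one. Report a defined evaluable set as a sensitivity analysis.

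In section 14.1, apply 11 or more of 25 to that set, and state the implied false-go probability of 0.098 beside the 0.79.

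This takes a few sentences, with no extra patients or procedures. If every treated patient is assessed, the results are identical. Otherwise the reported response rate may be slightly lower, and power falls as in step 5 when scans are missing for reasons unrelated to response. The change protects against bias and a denominator chosen late; it does not restore power.
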